10. ETHICAL AND REGULATORY REQUIREMENTS

10.1 Ethical conduct of the study

The study will be performed in accordance with ethical principles that have their origin in the Declaration of Helsinki and are consistent with ICH/Good Clinical Practice, applicable regulatory requirements and the AstraZeneca policy on Bioethics and Human Biological Samples.

10.2 Subject data protection

As previously described in Section 3.10, we have received a waiver of authorization for Horizon to share PHI with [REDACTED] for the purpose of the intervention and for Horizon to share a HIPAA limited dataset with [REDACTED] to conduct analyses on all identified intervention and control patients. The intervention itself poses no more than minimal risk because of the extensive security and privacy measures undertaken by the study team; any treatment decisions are also still being made by the patients' own physicians.

10.3 Ethics and regulatory review

An Institutional Review Board (IRB) from the [REDACTED] will approve the final study protocol, including any other written information and/or materials to be provided to the subjects. The Investigator will ensure the distribution of these documents to the applicable IRB Committee, and to the study site staff.

The opinion of the IRB Committee should be given in writing. The Investigator should submit the written approval to AstraZeneca before enrollment of any subject into the study. If required by local regulations, the protocol should be re-approved by the IRB Committee annually.

10.4 Informed consent

[REDACTED] will obtain verbal informed consent from patients prior to administering the intervention. All calls with patients, including those in which this consent is obtained, will be recorded and available for auditing.

10.5 Changes to the protocol and informed consent form

Study procedures will not be changed without the mutual agreement of the Principal Investigator and AstraZeneca.

If there are any substantial changes to the study protocol, then these changes will be documented in a study protocol amendment and where required in a new version of the study protocol (Revised Clinical Study Protocol).

The amendment is to be approved by the relevant Ethics Committee and if applicable, also the national regulatory authority approval, before implementation. Local requirements are to be followed for revised protocols.

AstraZeneca will distribute any subsequent amendments and new versions of the protocol to each Principal Investigator(s). For distribution to Ethics Committee see Section 10.3

If local regulations require, any administrative change will be communicated to or approved by each Ethics Committee.

10.6 Audits and inspections

Authorised representatives of AstraZeneca, a regulatory authority, or an Ethics Committee may perform audits or inspections at the centre, including source data verification. The purpose of an audit or inspection is to systematically and independently examine all study-related activities and documents, to determine whether these activities were conducted, and data were recorded, analysed, and accurately reported according to the protocol, Good Clinical Practice (GCP), guidelines of the International Conference on Harmonisation (ICH), and any applicable regulatory requirements. The Investigator will contact AstraZeneca immediately if contacted by a regulatory agency about an inspection at the centre.

1. STUDY DETAILS

1.1 Study objectives

The **primary objective** is to examine whether a two-stage process of shared decision-making and behavioral interviewing improves glycosylated hemoglobin (HbA1c) control and medication adherence among patients who have poorly-controlled diabetes.

The **secondary objective** is to develop prediction models and examine their ability to predict response to the study intervention based on baseline patient characteristics, such as sociodemographic, clinical, and medication use characteristics.

1.2 Study design

ENGAGE-DM (ENhancing outcomes through Goal Assessment and Generating Engagement in Diabetes Mellitus) is a pragmatic, prospective, intention-to-treat, randomized controlled trial designed to examine the impact of a novel intervention among patients with T2D that combines behavioral interviewing and shared decision-making delivered by pharmacists over the telephone compared with usual care. After the completion of the trial, we will examine whether a patient's response to the intervention could have been predicted based on their demographics, comorbidities or medication treatment-related factors.

This trial is being conducted among commercially-insured individuals whose medical and prescription benefits are administered by Horizon Blue Cross Blue Shield of New Jersey (Horizon). Horizon is the largest health insurer in New Jersey and administers plans for over 3.8 million beneficiaries.

Following the principles of pragmatic trial design, potentially eligible patients for inclusion in this study were those who: (1) were ≥ 18 years of age, (2) had filled a prescription for 1 or more oral hypoglycemic agents within the prior 12 months, and (3) had evidence of poor glycemic control (A1C $\geq 8\%$) within the previous 6 months, assessed using the most recent HbA1c lab values provided to Horizon Blue Cross Blue Shield. If patients had multiple HbA1c lab values, the latest value was evaluated. An HbA1c threshold of 8% was chosen based on the minimum threshold that nearly all patients should achieve based on guidelines from the American Diabetes Association (ADA); it is also a threshold for major quality measures for health plans. Patients were excluded if, prior to identification, they had fewer than 3 months of continuous enrolment in the health plan, had recently filled insulin (e.g., to exclude patients with type 1 diabetes), or had no available telephone contact information, which would preclude contact for enrolment and delivery of the intervention.

1.3 Number of subjects

In total, 1,400 subjects were randomized in a 1:1 ratio to the intervention or control group. Our study was designed to be sufficiently powered to detect small but clinically meaningful changes in the primary outcome of HbA1c change.

We considered the following assumptions in the power calculations. Assuming that 30% of study subjects in the intervention arm agree to participate in the intervention, we randomized 700 individuals

to each of the intervention and control groups in order to achieve 80% power to detect an average change in HbA1c of 0.5% between the intervention and control groups at an alpha threshold of 0.05 with a HbA1c standard deviation=1.9 (the most commonly cited value in the literature for HbA1c), accounting for 25% rate of loss-to-follow-up.^{1,2} We used Proc Power in SAS 9.4 (Cary, NC) using a t-test and adjusted the sample size to account for the reach rate. Because patients may change insurance, in particular at the end of the calendar year, we accounted for a rate of non-differential loss-to-follow-up of 25% rate. There may also be patients who do not have follow-up HbA1cs, despite restricting to patients whose providers have at-risk contracts with Horizon Blue Cross Blue Shield. As described later in Section 3, we will use multiple imputation methods to account for patients with no follow-up HbA1c values. In addition, this proportion of patients who agree to participate in this intervention has been observed in prior studies that have used a similar approach.²⁵ Finally, the proposed difference of HbA1c of 0.5% is the level that clinical guidelines consider to be a clinically meaningful difference in glycemic control. This HbA1c difference has also been observed in prior work with clinical pharmacists.⁸ Because the primary outcome is HbA1c change, we expect to see clinically meaningful differences in these levels within the 11 to 12-month follow-up period.^{3,4}

For secondary outcomes, with this sample size, we will also have the power to detect at least a 4% absolute difference in adherence (i.e., mean PDC levels) between the intervention and control groups, assuming baseline rates of adherence of 50%. We used Proc Power in SAS 9.4 (Cary, NC) using a chi-square test and adjusted the sample size to account for the reach rate. These differences in adherence have been observed as meaningful in prior research, and the baseline rate of adherence is based on prior research in this field.⁵⁻⁷ In addition, prescription claims will be captured on all patients included in the study by definition for inclusion, enabling the calculation of adherence in the follow-up period until loss of continuous eligibility. Therefore, there is no substantial lost-to-follow up expected for this outcome.

Finally, for the secondary objective (Aim 2), this sample size would also provide enough patients for the predictive modelling, given the relative non-rare nature of the study outcomes (glycemic control and medication adherence) and number of predictors considered per number of patients in the study.⁸

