8.1 Statistical considerations

Aim 1 (Primary Objective):

We have received Horizon Blue Cross Blue Shield Privacy Board approval to receive a HIPAA limited dataset on all patients for the purpose of analysis. The primary analyses will be conducted among all patients identified for the control group and the intervention group on an intention-to-treat basis. This approach will minimize the potential selection bias introduced by comparing only consenting patients to the identified controls, even if patients were carefully matched using observable covariates. Secondary analyses for all outcomes will be conducted among patients who provided informed consent versus the control group.

The primary outcome of interest will be the pre- to post-intervention change in mean HbA1c levels to the end of follow-up. Horizon BCBSNJ receives laboratory information from over 200 patient-centered medical homes and other population health programs and other practices. This laboratory information will be used to measure the change in HbA1c levels at the end of follow-up. Because the primary outcome is HbA1c change, we expect to see clinically meaningful differences in these levels within the 11 to 12-month follow-up period.^{24,25} We will use generalized estimating equations to compare the changes between the two study groups. Any observed imbalance between the groups will be controlled for using multivariable regression.

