2. ANALYSIS SETS

2.1 Definition of analysis sets

Full Analysis Set (Intention to Treat population): The primary and secondary outcomes will be evaluated using intention-to-treat principles among all randomized patients. Within the intervention group, patients who choose to speak with a pharmacist may differ from those who do not, and therefore an intention-to-treat analysis in this randomized study ensures unbiased comparisons to the control group. Therefore, the analysis set for the primary and secondary objectives will be the intention-to-treat population of all patients who meet inclusion and exclusion criteria and are randomized to the trial.

As-treated/per-protocol Analysis Set: We will also explore an “as-treated” analysis that compares patients in the intervention group who received the pharmacist intervention with patients in the usual care group. For this analysis set, the subgroup of patients in the intervention group who agreed to participate in the intervention will be compared against the patients in the control group. This analysis set will not be used for any of the primary analyses, only secondary analyses.

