4.2 Analysis methods

4.2.1 Primary objective (Effectiveness of intervention):

Baseline characteristics:

We will measure key baseline characteristics in the 12-months prior to randomization in the pharmacy and medical claims data and enrolment files. These characteristics will include sociodemographic characteristics, such as age and sex, which will be measured in the enrolment files. We will also measure baseline clinical characteristics such as the presence of coronary artery disease, chronic obstructive pulmonary disease, asthma, hypertension, hyperlipidemia, congestive heart failure, depression, liver disease, chronic kidney disease, osteoporosis and prior macrovascular complications. These will be measured in medical claims files using ICD-10 codes. We will also measure the type of oral glucose-lowering agent used in the baseline period (e.g., medical class), average PDC at baseline, and whether or not the medication is branded. We will also measure patients' latest copayments for oral glucose-lowering agents in the baseline period. Finally, we will also measure baseline healthcare resource utilization variables as characteristics including the number of days hospitalized and the number of physician office visits.

We will report, in tabular format, the means and frequencies of baseline characteristics prior to assignment separately for patients in the intervention and control groups and compare these values using t-tests, chi-square tests, and their non-parametric analogues, as appropriate. We will provide absolute standardized differences between the two treatment groups.

Primary analyses:

Primary outcome (change in HbA1c): In the primary analysis, the primary outcome, mean change in glycemic control, will be compared using generalized estimating equations with an identity link function (as a continuous variable) and normally distributed errors within the imputed full analysis set, as described above. Data will be presented as the unadjusted absolute difference in the change in HbA1c between the groups along with 95% confidence intervals.

Secondary outcome (proportion achieving glycemic control)

1) *Proportion of patients achieving optimal glycemic control* (defined by HbA1c < 8): This outcome will be compared using generalized estimating equations with a logit link and binary distributed errors. Data will be presented as the unadjusted odds ratio for optimal glycemic control between the groups along with 95% confidence intervals.

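### The stated 80% power for a 0.5% HbA1c difference comes from sizing reached patients against equal controls and is not the power of the intention-to-treat primary test

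*SAP*

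**What the plan says.** SAP 1.3 sets out the design: "Assuming that 30% of study subjects in the intervention arm agree to participate in the intervention, we randomized 700 individuals" to each group. The aim is "80% power to detect an average change in HbA1c of 0.5% between the intervention and control groups", at alpha 0.05 with SD 1.9 and 25% loss to follow-up. The size came from a t-test calculation, after which the authors "adjusted the sample size to account for the reach rate". The steps of that adjustment are not shown.

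Protocol 8.2 makes the same claim (at least 700 per group, 0.5%, SD 1.9, 80% power) but with a 45% rate, which it calls both the consent rate and the pharmacist contact rate. Table 5 shows the steps: a core size, a clustering factor of 1.03, division by one minus the loss rate, then division by the contact rate, ending at 696 per arm. The text adds that at least 236 of the 315 reached patients should have usable follow-up.

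Both documents make the primary analysis ITT. Protocol 8.1: "The primary analyses will be conducted among all patients identified for the control group and the intervention group on an intention-to-treat basis". SAP 2.1: "The primary and secondary outcomes will be evaluated using intention-to-treat principles among all randomized patients". SAP 4.2.1 runs the primary model "within the imputed full analysis set" and reports the "unadjusted absolute difference in the change in HbA1c between the groups along with 95% confidence intervals". Of the set that compares participants with controls, SAP 2.1 says: "This analysis set will not be used for any of the primary analyses, only secondary analyses".

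**The concern.** Dividing the sample size by the uptake rate secures a target number of participants. It does not reduce the expected effect for the patients in the intervention arm who never speak to a pharmacist, yet those patients are in the ITT comparison. The 80% therefore belongs to a contrast that the plan does not use as primary.

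Two further points follow. First, it is unclear what 0.5% refers to. The wording in both documents points to the difference between whole arms, but a reach adjustment makes sense only if 0.5% is the effect in those reached. Second, the two documents assume different uptake (45% and 30%) with the same 700 per arm and the same 80%. Each says that its rate was seen in earlier studies, and SAP section 6 lists no change from the protocol.

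What is at stake is how the primary result is read against the design. A null ITT result would be weighed against a stated 80% chance of finding 0.5%, and that chance could be far higher or far lower depending on what 0.5% means.

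**Working it through.** **Inputs.** 700 per arm, 0.5%, SD 1.9, alpha 0.05, 25% loss and 30% uptake (SAP 1.3); two-sided testing (SAP 4.1); 45% uptake, factor 1.03, loss range 15–30% and SD range 1.0–2.0 (protocol 8.2). Evaluable patients per arm: 700 × 0.75 = 525 (derived, not stated). Power is from the noncentral t; the normal formula, power ≈ Φ(δ / (SD × √(2/n)) − 1.96), agrees to within about 0.1 point.

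**1. The protocol's figure reproduces.** The core size for 0.5/1.9 at 80% power is 227.6, so 228. Then 228 × 1.03 = 235; 235 / 0.75 / 0.45 = 696. The contrast being sized is 525 × 0.45 = 236 reached patients against 236 controls, which has 81.4% power.

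**2. The SAP's figure does not follow from that method.** At 30%: 228 / 0.75 / 0.30 = 1,013.3, so 1,014 per arm; with the 1.03 factor, 1,043.7, so 1,044.

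**3. ITT power at 525 per arm.** The standard error is 1.9 × √(2/525) = 0.117.
- Whole-arm difference 0.5%: 0.5 / 0.117 = 4.26, power 98.9%. No reach adjustment is needed on this reading: 227.6 / 0.75 = 303.5, so 304 per arm would give 80%.
- Participants' effect 0.5%, none in others, 30% uptake: difference 0.30 × 0.5 = 0.15%, power 24.8%.
- The same at 45%: difference 0.45 × 0.5 = 0.225%, power 48.3%.

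**4. Sensitivity of ITT power** (each row changes one input from the base)

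| Setting | Whole-arm 0.5% | Participants 0.5%, 30% uptake | Participants 0.5%, 45% uptake |
|---|---|---|---|
| Base: n = 525, SD 1.9, no gain in others | 98.9% | 24.8% | 48.3% |
| 15% loss | 99.5% | 27.5% | 53.2% |
| 30% loss | 98.4% | 23.5% | 45.7% |
| All 700 informative | 99.8% | 31.4% | 60.0% |
| SD 1.0 | >99.9% | 68.0% | 95.4% |
| SD 2.0 | 98.2% | 22.9% | 44.5% |
| Others gain 0.1% | – | 46.6% | 66.5% |
| Others gain 0.2% | – | 69.5% | 81.4% |

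**5. What the ITT test can detect.** The difference with 80% power is (1.960 + 0.842) × 0.117 = 0.33% at 525 per arm. At 700 it is 2.802 × 1.9 × √(2/700) = 0.28%. If only participants respond, 0.329 / 0.30 = 1.10% or 0.329 / 0.45 = 0.73% in participants (at 525).

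**6. Gain in non-participants that restores 80%** when participants gain 0.5% (n = 525): (0.329 − 0.15) / 0.70 = 0.26% at 30% uptake; (0.329 − 0.225) / 0.55 = 0.19% at 45%.

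**Minor query.** Protocol 8.2 says that contacted patients need about 0.49% for an overall 0.5%. With 45% contacted, the rest would need (0.5 − 0.45 × 0.49) / 0.55 = 0.51%. The sentence cites Figure 3, which is not shown in the text available, so this is only a request to check.

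**The case against.** The strongest reply is that the claim, read as worded, understates the power: 0.5% between whole arms has about 99%. That stands. The adverse reading is inferred from the reach adjustment, not stated.

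Second, the protocol mails a decision aid to everyone allocated to the intervention, and its section 1.2 adds a pillbox. A zero effect in non-participants is therefore an assumption made here, not one taken from the documents. That also stands, although the documents give no figure for such an effect either.

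Third, the primary analysis imputes missing outcomes, so 525 may understate the information available. Multiple imputation does not in general restore what was lost; the 700-per-arm figures (31% and 60%) are upper bounds for loss alone.

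Fourth, randomization is complete, and the planned ITT difference with its 95% interval will show which effects remain compatible with the data, whatever the stated power. That is true, and it is why the remedy is limited to wording.

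A reader might infer more than the documents support:
- **That the trial is underpowered, or cannot have 80% power if 0.5% is the participants' effect.** Neither follows. The literal wording gives about 99%, and on the other reading a modest gain in non-participants or, at 45% uptake, an SD of 1.30 restores 80%.
- **That 25% and 48% are lower bounds.** They hold for 525 per arm, SD 1.9 and no gain in non-participants. SD 2.0 or 30% loss gives slightly less.
- **That the SAP's 700 is an arithmetic slip and should have been 1,014.** The SAP does not show its calculation, so the source of 700 at 30% uptake cannot be settled from the documents.

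**Conclusion.** The point holds as a fault in the design statement. The 80% describes a contrast of reached patients with an equal number of controls, as Table 5 of the protocol shows; it is not derived for the ITT primary test. At 525 evaluable per arm, SD 1.9 and two-sided 0.05, that test has about 99% power for a whole-arm 0.5%. For a 0.5% effect confined to participants it has about 25% (30% uptake) or 48% (45% uptake). Which applies depends on a definition that the plan does not give and on the effect in non-participants, which it does not quantify. The uptake rates also conflict between the documents at an unchanged 700 per arm and 80%, without explanation. The analysis itself is not in question. This should be fixed, but it does not threaten the validity of the primary comparison.

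**What to change.** In SAP 1.3, and in protocol 8.2 if the protocol is amended:

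- (a) State whether 0.5% is the difference between whole arms or the effect in participants.
- (b) Use one uptake rate, or explain the move from 45% to 30%. Show the calculation that leads to 700 and name the contrast it is for.
- (c) Replace the 80% claim with the ITT figure: 80% power for a whole-arm difference of about 0.33% at 525 evaluable per arm (about 0.28% at 700). At 525 this equals about 1.10% (30% uptake) or 0.73% (45%) in participants if others gain nothing. Add the sensitivity to the non-participant effect, the SD and the evaluable number.

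As a minor item, check the protocol's sentence on about 0.49% in contacted patients against Figure 3.

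The cost is a few sentences and a small table. No patients are added, and no estimand, model or test changes. The stated power becomes conditional on uptake and on the effect in non-participants. A change to the protocol text may need its amendment process; a clarification in the SAP alone would meet the main need.

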- 3) Loss-to-follow-up: Due to the potential for patients changing insurances particularly at the end of the calendar year, we anticipate that there could be some non-differential loss-to-follow-up of patients in the study. There may also be patients who do not have follow-up A1cs, despite restricting to patients whose providers have at-risk contracts with Horizon BCBS.
- 4) Pharmacist contact rate: We anticipate that approximately 45% of the patients will be reached by the pharmacists delivering the intervention.

Table 6. Justification: Adherence power calculation parameters and ranges

Range of parameters: input ranges	Difference in mean PDC: 5% Sample size (N range)/group
Baseline adherence: 50% --> N ₁	253
Intra-cluster correlation (N ₂ =N ₁ *1.03)	261
Loss-to-follow-up (LTF): 10-25% (N ₃ =N ₂ /[1-rate])	(best case: 290, worst case: 347)
Pharmacist contact rate: 35-50% (N ₄ =N ₃ /rate)	(best case: 580, worst case: 993)
Total	45% reach rate and 15% LTF: 682 patients/arm

[figure not shown]
Power (1-β): 0.80; Alpha (α): 0.05

Explanation of additional study parameters – Secondary outcome (Adherence)

- 1) Baseline adherence:
 - o 5% absolute difference in mean PDC has been seen in previous intervention studies and is considered to be a clinically meaningful difference^{16,24}
 - o Assuming ~50% baseline adherence based on previous literature²⁴
- 2) Loss-to-follow-up: Due to the potential for patients changing insurances, we anticipate there could be some non-differential loss-to-follow-up of patients in the study. Prescription claims will be captured on all patients included in the study by definition, enabling the calculation of adherence until loss of continuous eligibility.

Clinical Study Protocol
Drug Substance NA
Study Code D1843R00254
Edition 2
Date

Figure 3. Schematic of analytic plan

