3.3 Secondary outcome (two medication adherence outcomes):

Medication adherence will be measured using filling patterns in pharmacy claims data for medications that qualified a patient for inclusion in the study.¹³ For each medication, we will create a drug supply diary linking all observed fills after initiation based on dispensing date and days' supply. Different drugs in the same chemically-related therapeutic class (e.g., sulfonylureas) will be considered to be interchangeable. We will allow for up to 180 days of carryover supply. From these supply diaries, we will calculate the proportion of days that patients had medications available to them, or the proportion of days covered (PDC), by dividing the number of days with medication available by the number of days during follow-up.¹⁴ If a patient loses continuous eligibility during the year after the index date, the PDC will be calculated based on the number of days available. If a patient loses continuous eligibility during the year after the index date, they will be censored on that date, and the PDC will be calculated based on the number of days available. In this PDC measurement, if patients had at least one antidiabetic medication available, then they will be considered to be adherent for that day. This definition allows for outcome measurement even when patients switch (e.g., switch from metformin to a sulfonylurea) or intensify therapy (e.g., adding a second oral diabetes medication or injectable medication).

Using this PDC measure, we will observe *1) the mean PDC in each study arm* and *2) the proportion of patients achieving optimal adherence* (defined by ≥ 0.80 PDC) as adherence outcomes in the follow-up period. In a sensitivity analysis of this outcome, medication adherence will be measured by calculating the PDC beginning from the first fill of a medication after assignment until the end of the 12-month follow-up. There will be no missing data for these outcomes, as previously described.

These outcomes will be analysed formally.

3.4 Secondary analyses:

Resource utilization:

As secondary analyses, we will also measure healthcare spending and healthcare resource utilization, including outpatient visits, emergency room visits, and hospitalizations, in the follow-up period in the medical and pharmacy claims data. Healthcare spending will be measured as total allowed amounts in

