Secondary outcomes (medication adherence):

1) *Mean PDC in each study arm:* This outcome will be compared using generalized estimating equations with an identity link function and normally distributed errors. Data will be presented as the unadjusted absolute difference between the groups along with 95% confidence intervals.

2) *Proportion of patients achieving optimal adherence* (defined by ≥ 0.80 PDC): This outcome will be compared using generalized estimating equations with a logit link and binary distributed errors. Data will be presented as the unadjusted odds ratio for optimal adherence between the groups along with 95% confidence intervals.

Secondary analyses:

Healthcare resource utilization and spending: Secondary analyses of healthcare resource utilization will use a similar approach as the primary analysis among the full analysis set, except that we will use log link functions with Poisson errors to describe the count data. Health spending will also be evaluated with variances proportional to the mean (e.g., Poisson-like errors) using log-link functions in generalized estimating equations, which has been found to describe insurer healthcare spending data accurately based on prior research.⁵ Data will be presented as the unadjusted odds ratio along with 95% confidence intervals.

Adjusted analyses: If there are differences in baseline characteristics between study groups that are believed to be confounders (defined by a standardized mean difference of >0.1), we will repeat all of our analyses for the primary and secondary outcomes after adjusting for these covariates in multivariable regression. We will present these as adjusted effect estimates along with 95% confidence intervals.

Interactions: We will also explore any potential differences in effectiveness by the specific pharmacist delivering the intervention by evaluating effect measure modification and using interaction terms within the main model for the primary outcome of change in HbA1c. We will present p-values for interactions.

Subgroups: Subgroup analyses of the primary outcome (change in HbA1c) will also be performed for key subgroups, according to age, sex, depression, and baseline medication adherence levels. These analyses will be performed separately among subgroups of the characteristics and compared between the treatment arms. Data will be presented as unadjusted absolute differences in the change in HbA1c along with 95% confidence intervals.

Sensitivity analyses:

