6. CHANGES OF ANALYSIS FROM PROTOCOL

N/A

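### The 4-point detectable difference in mean PDC in SAP 1.3 does not follow from the chi-square method it names, or from Protocol Table 6, at 700 per arm and 30% uptake

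*SAP*

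**What the plan says.** SAP 1.3 claims "power to detect at least a 4% absolute difference in adherence (i.e., mean PDC levels) between the intervention and control groups", with baseline adherence of 50% and no substantial loss to follow-up for this outcome. On method it says: "We used Proc Power in SAS 9.4 (Cary, NC) using a chi-square test and adjusted the sample size to account for the reach rate". It gives no SD for PDC and no power level in this statement. The only uptake figure in SAP 1.3 comes with the HbA1c calculation: "Assuming that 30% of study subjects in the intervention arm agree to participate in the intervention".

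SAP 3.3 defines two adherence outcomes, mean PDC and the proportion with PDC of at least 0.80, and says of them: "These outcomes will be analysed formally". SAP 4.2.1 compares mean PDC using "generalized estimating equations with an identity link function and normally distributed errors".

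Protocol 8.2 planned on a larger difference and a higher uptake. Its rationale is that a "5% absolute difference in mean PDC has been seen in previous intervention studies". Table 6 starts from 253 per group for 5 points and ends at "45% reach rate and 15% LTF: 682 patients/arm". The SAP section headed "6. CHANGES OF ANALYSIS FROM PROTOCOL" reads N/A.

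**The concern.** A difference in means cannot be powered without an SD, and a chi-square test is not a test of means. The direction of change is also wrong. Under a reach adjustment, lower uptake raises the detectable difference. Between protocol and SAP the assumed uptake falls from 45% to 30%, yet the difference claimed for the same 700 per arm falls from 5 points to 4.

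Adherence is a secondary outcome, but it is named in the primary objective and will be tested formally. If the adherence result is null, readers will ask what difference the trial could have excluded. The answer depends on whether the 4 points refers to all randomized patients or only to those who took part, and on the SD. The statement settles neither.

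**Working it through.** **Inputs.** 700 per arm; two-sided alpha 0.05 (SAP 4.1); base rate 50%; no loss (SAP 1.3). Two inputs are inferred. Power of 80% comes from the HbA1c calculation in SAP 1.3 and the footnote to Table 6. Uptake of 30% is carried over from the HbA1c calculation, because the adherence statement mentions a reach rate without giving its value. The normal quantiles are 1.960 and 0.842, which sum to 2.802.

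**1. The method the SAP names: chi-square, 50% v 54%.**

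n = [1.960 × √(2 × 0.52 × 0.48) + 0.842 × √(0.50 × 0.50 + 0.54 × 0.46)]² / 0.04² = 2,448 per arm.

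- Power at 700 per arm is 32%.
- Applying the reach division as well gives 2,448 / 0.30 = 8,160 per arm.
- At 700 per arm and 80% power, the detectable difference is 7.5 points.

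The 4 points is not reproduced.

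**2. The method behind Protocol Table 6.** Chi-square does not reproduce Table 6 either, since 50% v 55% needs 1,565 per arm. A comparison of means does:

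- Implied SD = 0.05 × √(253/2) / 2.802 = 0.20.
- 253 × 1.03 = 261, and 261 / 0.85 / 0.45 = 682, the stated total.

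Applying that route with 30% uptake and no loss:

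- 4 points: a t-test at SD 0.20 needs 394 per arm, and 394 / 0.30 = 1,314. Scaling Table 6 directly gives 253 × (5/4)² / 0.30 = 1,318.
- Table 6's own 5 points: 253 / 0.30 = 843, or 261 / 0.30 = 870 with the clustering step. Both exceed 700.
- 700 × 0.30 = 210 per arm detects 5.5 points and has 53% power for 4.
- Reach needed for 4 points: 393 / 700 = 56%, outside Table 6's range of 35–50%. At 45% reach the detectable difference is 4.5 points, and at 50% it is 4.2.

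At SD 0.20, two one-sided variants come close to 4: 45% reach (3.97) and 210 participants against 700 controls (3.92). The SAP specifies two-sided tests. The second comparison is also not intention-to-treat, and done two-sided it detects 4.4 points.

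**3. What 700 per arm supports by intention to treat.** For a mean, the detectable difference is 2.802 × SD × √(2/700). SD 0.20 is back-calculated from Table 6; 0.25 and 0.30 are assumptions. The participant column divides by 0.30 and assumes no effect in patients not reached.

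| SD of PDC | Detectable, all randomized | Implied in participants at 30% uptake | Power for 4 points |
|---|---|---|---|
| 0.20 | 3.0 points | 10 points | 96% |
| 0.25 | 3.7 points | 12.5 points | 85% |
| 0.30 | 4.5 points | 15 points | 70% |

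- Power for 4 points stays at 80% or more up to SD 0.04 / (2.802 × √(2/700)) = 0.267. If the exclusions of up to 5% foreseen in SAP 2.2 occur (665 per arm), the limit is 0.260.
- If the 4 points is the effect in participants, the intention-to-treat difference is 4 × 0.30 = 1.2 points. Power is then 20% at SD 0.20 and 12% at SD 0.30, counting both rejection tails.
- For PDC of at least 0.80 at a 50% base rate, 700 per arm detects 7.5 points (7.7 at 665), or 7.5 / 0.30 = about 25 points among participants.

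The table omits Table 6's 1.03 clustering factor. Including it moves 3.00 to 3.04 points at SD 0.20.

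**The case against.** The strongest reply is that the SAP's claim is true, even conservative, at the only SD the documents imply. The statement speaks of a difference between the two groups, and SAP 2.1 analyses secondary outcomes in all randomized patients. Read that way, at SD 0.20, 700 per arm has 96% power for 4 points. This stands: the fault is in the justification, and the trial's capacity to detect 4 points has not been shown to be lacking. But it is not the calculation the SAP describes. The SAP says the sample size was adjusted for reach, which keeps the participant-level reading open, and the claim fails if the SD exceeds about 0.267.

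A second reply is that step 2 is a hybrid. The SAP does not say it used the Table 6 route, and the 30% is carried across from the HbA1c calculation. That is fair, and step 1 alone shows that the named method does not give 4 points. Step 2 shows only that the protocol's route does not give it either, and even at 50% reach with no loss it gives 4.2 points.

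A third is that revised planning assumptions are not a change of analysis, so the N/A in SAP section 6 may be defensible. That has some force, but the reader still needs to be told somewhere that the figures changed.

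**Conclusion.** The concern holds. The 4-point figure is attached to a test that does not fit mean PDC and has no SD behind it. It does not follow from the named method (7.5 points at 700 per arm), nor from the Table 6 route at 30% uptake (5.5 points). Depending on which meaning is intended, power for the stated 4 points is 70–96% or 12–20% over SDs of 0.20 to 0.30. These results assume 80% power, 30% uptake and, for the participant-level figures, no effect in patients not reached. The 32% power applies to the literal chi-square calculation only and should not be read as the trial's power for mean PDC. The point concerns the planning statement for secondary outcomes; the HbA1c calculation is a separate matter.

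**What to change.** Rewrite the adherence part of SAP 1.3 on the intention-to-treat scale, at a stated 80% power, with one figure per outcome:

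- **Mean PDC:** a two-sample t-test with a stated and sourced SD. With 700 per arm this gives 3.0, 3.7 or 4.5 points at SD 0.20, 0.25 or 0.30. Keep the 4 points only as an intention-to-treat difference, with a justified SD of about 0.267 or less (0.260 if 5% are excluded).
- **PDC of at least 0.80:** its own chi-square figure, about 7.5 points at a 50% base rate.
- **Reach:** drop the division by reach. Report instead the effect in participants that each figure implies at 30% uptake: 10 to 15 points for mean PDC and about 25 points for the proportion.
- **Change record:** correct Table 6 in the same way, or say in the SAP that it is superseded. Note the move from 5 points at 45% uptake to 4 points at 30% in SAP section 6.

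The cost is wording. Randomization is complete, so no patients are added, and the analysis does not change. The restated figure may be less favourable than 4 points if the sourced SD is large, or more favourable if it is near 0.20.
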